2.1 Objectives

Primary Objectives

Part A: To determine the recommended phase 2 dose and schedule of ¹⁷⁷Lu-PSMA-617 in combination with pembrolizumab in patients with mCRPC.

Part B (Dose Expansion): To determine the objective response rate by RECIST 1.1 criteria.

Secondary Objectives

1. To characterize the safety profile of the combination.
2. To determine the median duration of response by RECIST 1.1 criteria.
3. To determine the proportion of patients who experience $\geq 50\%$ decline from baseline in serum PSA.
4. To determine the median PSA progression-free survival.
5. To determine the median time to symptomatic skeletal related event.
6. To determine the 6 month radiographic progression-free survival rate and median radiographic progression-free survival.
7. To determine the median overall survival.

Correlative Objectives

1. To assess the lesion-specific response rate by baseline PSMA avidity on ⁶⁸Ga-PSMA-11 PET.
2. To quantify the change from baseline in T cell repertoire, circulating T cell subsets, tumor infiltrating lymphocytes, and tumor PD-L1 expression by immunohistochemistry after one priming dose of Lu-PSMA RLT.
3. To explore the relationship between timing of the ¹⁷⁷Lu-PSMA-617 priming dose with initiation of pembrolizumab with respect to immunologic, safety, and efficacy outcomes.
4. To descriptively characterize the patterns of uptake on ⁶⁸Ga-PSMA-11 PET at the time of disease progression.
5. To explore relationship between tumor genomic profile with clinical outcomes including response rate and progression-free survival.
6. To explore the relationship between tumor dosimetry with objective response.

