2.2 Endpoints

2.2.1 Primary Endpoint

Part A: Safety profile of ¹⁷⁷Lu-PSMA-617 in combination with pembrolizumab as graded by CTCAE criteria.

Part B: Objective response rate by RECIST 1.1 criteria

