2.2.2 Secondary Endpoints

1. Frequency and severity of adverse events as defined by CTCAE criteria.
2. Median duration of response by RECIST 1.1
3. PSA response rate
4. Radiographic progression-free survival rate at 6 months and median radiographic progression-free survival.
5. Overall survival

3 Study Design

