3.2 Randomization

There is no randomization for the study.

During Part A of the study, patients will be enrolled in sequential fashion to one of three dosing schedules of ^{177}Lu -PSMA-617 as outlined above. 6 patients will be enrolled to Schedule 1, followed by 6 patients enrolled on Schedule 2, and then 6 patients will be enrolled on Schedule 3.

During Part B of the study, all patients enrolled will receive the recommended phase 2 dose and schedule of ^{177}Lu -PSMA-617 plus pembrolizumab.

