6.3.2.5 Attribution of Adverse Events

The toxicity profiles of the two investigational agents are largely non-overlapping, which should facilitate adverse event attribution to the specific agent. Hematologic toxicity will be attributed to Lu-PSMA-617 unless there is clear evidence of autoimmune cytopenia. Xerostomia will be attributed to Lu-PSMA-617 unless clear evidence of other autoimmune sequelae. Conversely, immune-related AEs such as colitis, pneumonitis, transaminitis will be attributed to pembrolizumab. In cases where attribution to a specific agent is not possible, the timing of onset in relation to timing of initiation of Lu-PSMA and pembrolizumab will be utilized. In cases where adverse event attribution to a single agent is not possible, attribution will be to study regimen

and dose modification criteria for both agents will be utilized. The PI will have the final determination of adverse event attribution that is reported.

AEs associated with pembrolizumab exposure, including coadministration with additional compounds, may represent an immunologic aetiology. These immune-related AEs (irAEs) may occur shortly after the first dose or several months after the last dose of pembrolizumab/combination treatment and may affect more than one body system simultaneously. Therefore, early recognition and initiation of treatment is critical to reduce complications. Based on existing clinical study data, most irAEs were reversible and could be managed with interruptions of pembrolizumab/combination treatment, administration of corticosteroids and/or other supportive care. For suspected irAEs, ensure adequate evaluation to confirm etiology or exclude other causes. Additional procedures or tests such as bronchoscopy, endoscopy, skin biopsy may be included as part of the evaluation. Dose modification and toxicity management guidelines for irAEs associated with pembrolizumab/combination treatment are provided in AE Table.

Attribution of Toxicity:

When study interventions are administered in combination, attribution of an adverse event to a single component is likely to be difficult. Therefore, while the investigator may attribute a toxicity event [to the combination, to ¹⁷⁷Lu-PSMA-617 alone or to pembrolizumab alone, for adverse events listed in AE Table 6, both interventions must be held according to the criteria in AE Table Dose Modification and Toxicity Management Guidelines for Immune-Related Adverse Events Associated with Pembrolizumab.

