6.4 Recording of an Adverse Event

All grade 3 and above adverse events will be recorded using the NCI CTCAE v4.0. The Investigator will assign attribution of the possible association of the event with use of the investigational drug.

Relationship	Attribution	Description
Unrelated to investigational drug/intervention	Unrelated	The AE is clearly NOT related to the intervention
	Unlikely	The AE is doubtfully related to the intervention
Related to investigational drug/intervention	Possible	The AE may be related to the intervention
	Probable	The AE is likely related to the intervention
	Definite	The AE is clearly related to the intervention

Signs or symptoms reported as adverse events will be graded and recorded by the Investigator according to the CTCAE. When specific adverse events are not listed in the CTCAE they will be graded by the Investigator as *none*, *mild*, *moderate* or *severe* according to the following grades and definitions:

- Grade 0 No AE (or within normal limits)
- Grade 1 Mild; asymptomatic or mild symptoms; clinical or diagnostic observations only; intervention not indicated
- Grade 2 Moderate; minimal, local, or noninvasive intervention (e.g., packing, cauter) indicated; limiting age-appropriate instrumental activities of daily living (ADL)
- Grade 3: Severe or medically significant but not immediately life-threatening; hospitalization or prolongation of hospitalization indicated; disabling; limiting self-care ADL
- Grade 4: Life-threatening consequences; urgent intervention indicated
- Grade 5: Death related to AE

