8.4.2 Analytic Plan for Secondary Endpoints

Median duration of response

Median duration of response will be estimated using Kaplan-Meier product limit method, starting with the date of first scan indicating response until loss of response or progression, or death, whichever occurs first.

PSA response rate

The proportion of patients who achieve a greater than 50% decline from baseline PSA drawn on C1D1, at any point in the treatment course, will be descriptively reported along with 95% confidence interval.

PSA progression free survival

PSA progression will be defined using PCWG3 criteria. Median PSA progression free survival will be estimated using the Kaplan-Meier method. Duration will be measured from date of first treatment to date of first PSA meeting criteria for PSA progression.

Time to symptomatic skeletal related event

Symptomatic skeletal related event is defined as the first occurrence of one or more of the following: symptomatic fracture, surgery or radiation to bone, or spinal cord compression. The median time to symptomatic skeletal related event will be determined using Kaplan-Meier method.

Safety

The incidence and severity of adverse events related to study treatment will be descriptively reported using CTCAE v4.0.

Radiographic progression free survival and 6-month rPFS rate:

Radiographic progression of disease will be defined by RECIST v1.1 and PCWG3 criteria. For the first scheduled reassessment by bone scan (at Cycle 2), new bone lesions will require a confirmatory bone scan 6 or more weeks later. Median PFS will be estimated using the Kaplan-Meier method. Durations will be measured from the first day of study treatment (Cycle 1) to the first date of radiographic progression or death, whichever occurs first. Patients who discontinue study treatment for toxicity, withdraw from the study, or have PSA-only progression will be censored at the date of the last radiographic tumor assessment. Patients who discontinue treatment for clinical progression or deterioration will be included in the analysis.

Overall survival

Median overall survival and 95% confidence interval will be estimated using the Kaplan-Meier method. Duration will be measured from first date of study therapy to date of death from any cause.

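### Section 8.4.2 plans a summary of treatment-related adverse events only, although the safety endpoints it serves cover adverse events regardless of cause

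*Combined protocol and SAP*

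**What the plan says.** Section 8.4.2 has one sentence on safety: "The incidence and severity of adverse events related to study treatment will be descriptively reported using CTCAE v4.0".

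The endpoints and objective that this sentence has to serve carry no relatedness condition:

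- Section 2.2.2, first secondary endpoint: "Frequency and severity of adverse events as defined by CTCAE criteria".
- Section 2.2.1, Part A primary endpoint: the safety profile of 177Lu-PSMA-617 "in combination with pembrolizumab as graded by CTCAE criteria".
- Section 2.1, first secondary objective: "To characterize the safety profile of the combination".

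On who decides relatedness, section 6.4 says "The Investigator will assign attribution of the possible association of the event with use of the investigational drug", and section 6.3.2.5 adds "The PI will have the final determination of adverse event attribution that is reported". Section 4.4 states that the trial is open-label. Section 3.2 states "There is no randomization for the study". Part A enrolls three schedule cohorts one after another, and Part B is a single expansion cohort.

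**The concern.** The plan names an endpoint that counts adverse events of any cause and then specifies an analysis of a subset of them. Membership of the subset depends on a judgement made with full knowledge of treatment. There is no concurrent control against which to judge how often such events would occur anyway.

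Safety is the Part A primary endpoint and one of the grounds for choosing the dose and schedule. Under the Abstract the principal investigator makes that choice; under section 3.1 the DSMC does so together with the principal investigator. The person with the final say on attribution therefore also takes part in the selection. A later reader who has only the related-event table could not separate the toxicity observed from the attribution applied to it. A correlative objective in section 2.1 also explores safety in relation to the timing of the priming dose. With 6 patients per schedule, moving one patient in or out of a table changes an incidence by 1/6 = 16.7 percentage points.

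**Working it through.** The plan gives no figure for this analysis, so there is nothing to reproduce. The check compares texts, followed by a short piece of arithmetic on direction.

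**Step 1. Set the event sets side by side.**

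| Place | Events covered |
|---|---|
| 2.2.2, first secondary endpoint | adverse events, no relatedness filter |
| 2.2.1, Part A primary endpoint | safety profile, no relatedness filter |
| 2.1, first secondary objective | safety profile, no relatedness filter |
| 8.4.2, safety analysis | related events |

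**Step 2. Look for an all-cause summary elsewhere.** Section 8.4.1 bases the Part A recommendation on the safety and efficacy data taken together, but specifies no tabulation. Section 6.2 fixes the patients (those who receive the radiotracer) and the grading system, not the set of events. Appendix 2 has Grade 3 to 5 events entered in the trial database whatever their attribution and reviewed monthly. That is monitoring, not a planned analysis. No sentence in section 8 plans an all-cause summary.

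**Step 3. Direction.** Related events are a subset of all events. A patient's maximum related grade cannot exceed the maximum all-cause grade, and related incidence cannot exceed all-cause incidence. For a given event category, let T be the all-cause incidence and u the share of affected patients whose events are all called unrelated. Then

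reported incidence = T × (1 − u).

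Any error in T from using the related-only table is therefore downward, and it is zero if u = 0.

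**Step 4. Illustration of size.** The documents give neither T nor u. The values below are assumptions, applied to the planned 43 patients (18 + 25).

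| Assumed T | Patients affected | u = 10% | u = 25% | u = 50% |
|---|---|---|---|---|
| 30% | 43 × 0.30 = 12.9 | 27% (11.6) | 22.5% (9.7) | 15% (6.5) |
| 50% | 43 × 0.50 = 21.5 | 45% (19.4) | 37.5% (16.1) | 25% (10.8) |

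The gap runs from 3 points (30 − 27) to 25 points (50 − 25) over this grid. The grid shows how the result depends on u. It is not an estimate for this trial.

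**Step 5. What holds u down.** Section 6.4 places the category Possible, with Probable and Definite, on the related side, so only events called Unrelated or Unlikely are lost. Section 6.3.2.5 attributes hematologic toxicity to 177Lu-PSMA-617 unless there is clear evidence of autoimmune cytopenia, so u should be small for that class.

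**Step 6. Can an all-cause table be produced?** The safety assessments in the Abstract have all adverse events, serious or not, on therapy or within 30 days of the last dose recorded on case report forms. Section 6.4 speaks of recording Grade 3 and above. Under either reading Grade 3 to 5 events of any cause are captured, and Appendix 2 confirms this. Grade 1 and 2 events are assured only if the Abstract governs.

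**The case against.** The best defense is that 8.4.2 describes a descriptive secondary summary and does not forbid others. The Part A recommendation under 8.4.1 draws on all safety data, and no stopping or dose rule uses the 8.4.2 table. The hematologic dose-limiting toxicity criteria in section 4.1.6 carry no relatedness condition. All-cause rates in advanced prostate cancer also include events of the disease and can overstate drug toxicity. Most of this stands: it limits the consequence, and it is a reason to keep a related-event table. It does not supply the missing analysis of the stated endpoint.

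Three stronger readings are tempting and are not supported:

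- A reader might infer that toxicity will be understated. The documents show only that it can be. If few events are called Unrelated or Unlikely, the loss is small.
- A reader might take a size from the platelet row of the earlier phase 2 study's hematology table in section 1.7.1. The columns of that table cannot be assigned reliably in the text available. The row also concerns a toxicity class that this protocol counts as related by default.
- A reader might cite the remark in section 6.3.2.5 that "attribution of an adverse event to a single component is likely to be difficult". It concerns which of the two drugs caused an event. The same section assigns unresolved cases to the regimen, so they remain related to study treatment. The remark does not show that events drop out.

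**Conclusion.** The point holds as a mismatch between endpoint and analysis. The one adverse event summary planned in section 8 covers related events, while the secondary endpoint, the Part A primary endpoint and the first secondary objective are unfiltered. Followed as written, the plan leaves the stated endpoint unanalyzed and makes the reported rates depend on an open-label judgement without a concurrent control. The three Part A cohorts do not act as one, because all of them receive both drugs.

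The direction of any error is fixed (downward relative to all-cause incidence). Its size is unknown, and the attribution rules in sections 6.3.2.5 and 6.4 limit it. The conclusion rests on reading the 8.4.2 sentence as the whole planned summary, which is how section 8 stands. It does not touch the Part B response-rate analysis or its sample size.

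**What to change.** State in 8.4.2 that all treatment-emergent adverse events will be tabulated by maximum grade, by part and by schedule, regardless of attribution, with related events in a second table of the same layout. Define treatment-emergent, including the start and end of the reporting window; the Abstract already gives 30 days after the last dose for recording.

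Reconcile the Abstract with section 6.4 on which grades are recorded. If all grades are kept, the main table can show all grades. If only Grade 3 and above are kept, the all-cause table should be limited to Grades 3 to 5 and labelled so.

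This is a cheap improvement. It costs one extra table and one clarification of the recording rule, with no change to sample size or significance level. The drawback is that all-cause rates include disease-related events, which is why both tables are kept.

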Grades 3 or 4	Stop Infusion. Grade 3: Prolonged (i.e., not rapidly responsive to symptomatic medication and/or brief interruption of infusion); recurrence of symptoms following initial improvement; hospitalization indicated for other clinical sequelae (e.g., renal impairment, pulmonary infiltrates) Grade 4: Life-threatening; pressor or ventilatory support indicated	No subsequent dosing Additional appropriate medical therapy may include but is not limited to: IV fluids Antihistamines NSAIDS Acetaminophen Narcotics Oxygen Pressors Corticosteroids Epinephrine Increase monitoring of vital signs as medically indicated until the subject is deemed medically stable in the opinion of the investigator. Hospitalization may be indicated. Subject is permanently discontinued from further trial treatment administration.
Appropriate resuscitation equipment should be available in the room and a physician readily available during the period of drug administration.		

5 Study Procedures

A written, signed, informed consent form (ICF) and a Health Insurance Portability and Accountability Act (HIPAA) authorization must be obtained before any study-specific assessments are initiated. A copy of the signed ICF will be given to the subject and a copy will be filed in the medical record. The original will be kept on file with the study records.

The Study Calendar summarizes the trial procedures to be performed at each visit according to the assigned Treatment Schedule (Schedule 1, Schedule 2, or Schedule 3, respectively). Screening assessments must be performed within 28 days prior to the initiation of protocol therapy. Any results falling outside of the reference ranges may be repeated at the discretion of the investigator. All on-study procedures are allowed a window of \pm 3 days unless otherwise noted. Treatment or visit delays for public holidays or weather conditions do not constitute a protocol violation.

Individual trial procedures are described in the study schedule below. It may be necessary to perform these trial procedures at unscheduled time points if deemed clinically necessary by the investigator.

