5.1 Discontinuation of Therapy

Study treatment will be discontinued at the first occurrence of one of the following:

- Radiographic progression by RECIST 1.1/PCWG3 criteria, confirmed by repeat scans performed at least 4 weeks following first scans showing progression.
- Unequivocal clinical progression

Note: Patients without clinical or radiographic evidence of disease progression, with PSA-only progression, should continue to receive protocol therapy.

- Unacceptable toxicity (as described in section 4.8)
- Recurrent Grade 2 pneumonitis
- Patient withdrawal from study
- Investigator withdrawal of patient due to concerns for patient compliance with study protocol procedures
- Receipt of non-protocol systemic anti-prostate cancer therapy
- Death
- Completion of 35 treatments (approximately 2 years) with pembrolizumab

Note: The number of treatments is calculated starting with the first dose. Participants who stop the combination or pembrolizumab after receiving 35 doses may be eligible for retreatment if they progress after stopping study treatment provided they meet the requirements detailed below. Participants may be retreated in the Second Course Phase (Retreatment) for up to an additional 17 cycles (approximately 1 year).

Second Course of Pembrolizumab *

All participants who stop study treatment with SD or better may be eligible for up to an additional 17 cycles (approximately 1 year) of pembrolizumab treatment if they progress after stopping study treatment from the initial treatment phase. This retreatment is termed the Second Course Phase of this study and is only available if the study remains open and the participant meets the following conditions:

Either

- Stopped initial treatment with study treatment after attaining an investigator-determined confirmed CR based on RECIST 1.1, and
 - Was treated with at least 8 cycles of study treatment before discontinuing treatment, and
 - Received at least 2 treatments with pembrolizumab beyond the date when the initial CR was declared

OR

- Had SD, PR, or CR and stopped study treatment after completion of 35 administrations (approximately 2 years) of study treatment for reasons other than disease progression or intolerance

AND

- Experienced an investigator-determined radiographic disease progression by RECIST 1.1 after stopping initial treatment, and
- No new anticancer treatment was administered after the last dose of study treatment, and

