5.2 Study Calendar: Schedule 1 (¹⁷⁷Lu-PSMA-617 prior to Pembrolizumab)

	Screening (Day -28 to -1 unless otherwise noted)	Treatment				End of Treatment	Safety Follow up			
		Cycle 1			Cycle 2+ (+/- 3 days unless otherwise noted)		D1 (+/- 3 days)	+ 21 days	30 Days (+/- 7 days) post-last dose	
		D1 (-3 days)	D2	D8 (+/- 1 day)						
Informed consent	x									
Medical history	x									
Baseline conditions	x									
Concurrent medications	x	x		x	x	x	x	x	x	
Height	x									
Weight	x	x		x	x	x	x	x	x	
ECOG Performance status	x	x		x	x	x	x	x	x	
Physical exam and vital signs	x	x		x	x	x	x	x	x	
CBC and Serum Chemistry Panel^{1,2}	x	x		x	x	x ³	x	x	x	
Thyroid function tests^{2,4}	x					x	x	x	x	
PSA²	x	x				x	x	x	x	
Testosterone	x									
⁶⁸Ga-PSMA-11 PET/CT or PET/MR	x ⁵						x			
Disease assessment	x					x	x			

¹ Chemistry panel to include: sodium, potassium, chloride, bicarbonate, BUN/creatinine, glucose, calcium, total bilirubin, AST, ALT, alkaline phosphatase

² Labs may be collected within a window of up to 3 days prior to each dose of pembrolizumab.

³ CBC + differential will be measured on C1D1, C1D8, C1D15, C2D1, C2D8, C2D15, Day 1 of C3+, and additionally as clinically indicated.

⁴ TSH (with reflex free T3/T4) testing to be performed during Screening, Cycle 2 Day 1, and Day 1 of every other cycle thereafter.

⁵ Allow for a 12-week window for the screening PSMA PET scan. PSMA PET at End of Treatment is optional.

	Screening (Day -28 to -1 unless otherwise noted)	Treatment				End of Treatment	Safety Follow up		
		Cycle 1			Cycle 2+ (+/- 3 days unless otherwise noted)		30 Days (+/- 7 days) post-last dose	90 Days (+/- 14 days) post last dose	
		D1 (-3 days)	D2	D8 (+/- 1 day)	D15 (+/- 1 day)	D1 (+/- 3 days)	+ 21 days		
(CT/MR, BS) ⁶									
Tumor Biopsy ⁷	x				x				
Whole blood for immune correlatives ⁸		x			x	x			
¹⁷⁷ Lu-PSMA-617 infusion		x							
SPECT/CT Dosimetry ⁹			x						
Normal Saline		x							
Anti-emetic pre-medication		x							
Pembrolizumab infusion					x				
AE assessment		x	x	x	x	x	x	x	x

⁶ Tumor assessment will be performed with CT chest/and/pelvis + whole body bone scan during Screening, C4D1 (-14d), C7D1 (-14d), and Day 1 (-14d) of every 4 cycles thereafter. If disease progression by RECIST 1.1/PCWG3, confirmatory scans are required \geq 4 weeks following first scan showing progression.

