7.6 Evaluation of non-measurable bone disease per PCWG Criteria

Bone scans obtained after the baseline evaluation will be used to evaluate post-treatment changes. Bone scans obtained will be evaluated as either "no new lesions" or "new lesions" on the tumor measurement forms.

- For the first scheduled reassessment: New lesions at the first scheduled evaluation (9 weeks) will require a confirmatory bone scan 6 or more weeks later. If no new lesions are observed on the confirmatory bone scan, study therapy is continued. If additional new lesions are observed, then the patient has experienced progression. Progression in this situation is dated as the time of the first reassessment scan.

- b. For subsequent scheduled reassessments: If no new lesions are observed, study therapy will continue. If new lesions are observed, this is evidence of disease progression. Date of progression is the date at which the scan was obtained.

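### Overall survival has no contact after the 90-day visit and no censoring rule; smaller points are an unqualified 6-month rPFS rate and a mislabelled bone scan in 8.4.2

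*Combined protocol and SAP*

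**What the plan says.** **Overall survival.** Section 2.2.2 lists OS as a secondary endpoint. Section 8.4.2 estimates its median by Kaplan-Meier, from first study therapy to death from any cause, and does not say when a living patient is censored. The last contact planned for everyone is a safety visit at about 90 days, counted from the End of Treatment visit in the synopsis and from the last dose in the calendars (5.2 to 5.4). Two provisions go further, but neither is survival follow-up. Section 4.8 follows patients who stop for a prolonged immune-related event only until progression or other therapy. The second course in 5.1 covers only retreated patients.

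**6-month rPFS.** Section 2.2.2 names "Radiographic progression-free survival rate at 6 months and median radiographic progression-free survival". Footnote 6 of all three calendars sets scans at Screening and then "C4D1 (-14d), C7D1 (-14d), and Day 1 (-14d) of every 4 cycles thereafter". Section 8.4.2 gives rPFS a Kaplan-Meier estimate and a censoring rule, but no sensitivity estimate. Some progression can be found between routine scans. Section 5 says "It may be necessary to perform these trial procedures at unscheduled time points if deemed clinically necessary by the investigator", and 8.4.2 says "Patients who discontinue treatment for clinical progression or deterioration will be included in the analysis".

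**Bone-scan rule.** Section 8.4.2 reads "For the first scheduled reassessment by bone scan (at Cycle 2), new bone lesions will require a confirmatory bone scan" (at least six weeks later). Section 7.6(a) reads "New lesions at the first scheduled evaluation (9 weeks) will require a confirmatory bone scan 6 or more weeks later". For later scans, 7.6(b) says "If new lesions are observed, this is evidence of disease progression".

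**The concern.** Study treatment normally stops soon after confirmed progression, so scheduled contact ends about three months after that. The patients who leave view are then mostly those who have just progressed. If progression predicts death, censoring them at that point is informative and the Kaplan-Meier median is too long. Whatever the censoring rule, deaths after the last visit are not systematically collected.

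For rPFS, a progression at week 20 that is found only by a routine scan is dated at week 28 to 30, so the patient still counts as progression-free at 6 months. The error is upward.

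The bone-scan label matters because 8.4.2 is the section that defines the rPFS analysis, and it names a scan that does not exist.

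The synopsis says that favourable safety and preliminary efficacy would form the basis of a definitive randomised study, so flattering OS or rPFS figures could carry forward.

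**Working it through.** **Calendar.** Cycles last 21 days, so Day 1 of cycle k falls (k-1) x 21 days after C1D1.

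- Cycle 2 covers days 21 to 41. No scan is listed there.
- C4D1 = 3 x 21 = day 63 = week 9. This reproduces the 9 weeks in 7.6(a).
- C7D1 = day 126 (week 18); C11D1 = day 210 (week 30).
- With the 14-day early window, routine scans fall at weeks 7-9, 16-18 and 28-30.
- Six months = 365.25/2 = 182.6 days = week 26.1, inside the last gap.
- In Schedule 3 the first dose is on Cycle 1 Day -21, which adds three weeks: weeks 10-12, 19-21 and 31-33. Six months is again in a gap.

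**OS illustration.** The 12.7-month median comes from section 1.3 (the cited Lu-PSMA monotherapy study). Accrual of 21 months within 36 (8.2) leaves 36 - 21 = 15 to 36 months of follow-up, taken as uniform. Everything else is assumed. Model A is exponential time to progression followed by exponential post-progression survival. Model B has independent exponential progression and death. Contact ends at the detecting scan + 28 days (confirmatory scan) + 90 days from last dose, or with a further 21 days if the 90 run from the End of Treatment visit. Treatment is capped at 35 doses. Model A gives:

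| Assumed median time to progression (months) | 4 | 6 | 8 |
|---|---|---|---|
| 90 days from End of Treatment visit: OS median (months); deaths of 43 | 14.3; 19 | 14.4; 23 | 14.0; 26-27 |
| 90 days from last dose: OS median (months); deaths of 43 | 15.0; 17 | 15.2; 21 | 14.7; 25 |
| Vital status to study close: OS median (months); deaths of 43 | 12.7; about 35 | 12.7; about 35 | 12.7; about 35 |

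Medians carry simulation error of about 0.1 month. If half of progressions are found at once, contact ends sooner and the censored medians are 14.6 to 15.9 months. A starker model, in which contact ends 90 days after treatment with no wait for a scan or its confirmation and no study close, gives 17.6 to 19.7. Model B gives 12.6 to 12.7, that is, no bias; with vital status to close it yields about 32 deaths.

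**6-month rPFS illustration.** Take exponential rPFS with a 6-month median, so the true rate at day 182.6 is 50%. If every event were dated at a routine scan, the curve at 6 months would show its value at the previous scan:

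- week 18: 0.5^(126/182.6) = 62%
- week 16: 0.5^(112/182.6) = 65%

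Deaths before the next scan count on their own dates and reduce this. Models A and B with OS medians of 12.7 and 20 months, and scans 0 to 2 weeks early, give:

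| Share of progression found at once, off-calendar | Schedules 1 and 2 | Schedule 3, from Day -21 |
|---|---|---|
| None | 57-63% | 54-58% |
| Half | 53-56% | 52-54% |
| Three quarters | 52-53% | 51-52% |

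Over median rPFS of 4 to 10 months, the Schedule 1 and 2 excess is 2-15, 1-7 and 0.5-4 points respectively. The 95% CI half-width is 1.96 x sqrt(0.25/N): 19.6 points at N = 25 and 14.9 at N = 43.

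**What a sensitivity estimate would recover.** An interval-censored Weibull fit was simulated in 300 trials of 43 patients (model A, true 50%) under exponential, lognormal and durable-responder truths:

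| | Interval-censored | Kaplan-Meier |
|---|---|---|
| All found on routine scans | 51, 55, 53% | 62, 65, 60% |
| Half found at once, entered at their own dates | 51, 55, 53% | 56, 58, 55% |
| Half found at once, but entered as intervals | 47, 52, 49% | - |

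**The case against.** **OS.** No text censors OS at the last scheduled visit, and date last known alive is the usual default. The 12.7 months comes from monotherapy in another trial, and Model B shows no bias. All of this stands, so the 14 to 15 months is conditional and illustrative. It does not answer the missing contact: without later checks, the date last known alive will often be close to the last visit, and later deaths are found only by chance.

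**rPFS.** Dating progression at the detecting scan is conventional. PSA and clinical review occur each cycle, unscheduled procedures are allowed, and clinical deterioration counts. The error lies within the confidence interval and no decision rests on it. This also stands. With half found off-calendar, the sensitivity estimate removes only 2 to 5 points (58 - 55 = 3, for example). That supports adding one estimate, not changing the scan calendar or the main analysis.

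**Bone-scan rule.** A reader might infer that, because no Cycle 2 scan exists, C4D1 becomes a later scan at which 7.6(b) counts new lesions as progression at once, which would lower the 6-month rate. The documents do not support this: 7.6(a) expressly gives the confirmation rule to the 9-week scan, which is C4D1. A reader might also see a conflict between the six-week bone rule and 5.1, where progression is "confirmed by repeat scans performed at least 4 weeks following first scans showing progression". A scan at six weeks or later meets both, and 5.1 concerns stopping treatment rather than the endpoint.

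**Conclusion.** The point holds as two inexpensive improvements and one wording correction.

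- **OS (main point).** Survival contact and a censoring rule are absent from the available text. On the assumed models, roughly half to three quarters of the deaths otherwise available would be seen (17/35 = 49% to 27/35 = 77%). A bias of about 1 to 2.5 months arises only if OS is censored at last scheduled contact and progression predicts death.
- **6-month rPFS.** The error is upward: 7 to 13 points at a true 50% with routine-scan detection only, and 2 to 6 if half or more is found off-calendar. The off-calendar share is not documented.
- **Bone-scan label.** This is a conflict between 8.4.2 on one side and 7.6(a) with footnote 6 on the other. The rule itself is present in 7.6(a), and no effect on the estimate is claimed.

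All three concern descriptive secondary endpoints. The Part B response-rate analysis and the safety rules are untouched.

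**What to change.** 1. Collect vital status by chart review or telephone about every 12 weeks to study close, and state in 8.4.2 that OS is censored at the date last known alive. Chart review can also cover patients already past their last visit. This fits the planned 36 months.
2. Keep the scan calendar and the 6-month Kaplan-Meier rate. Add one sensitivity estimate in which progression found on routine scans is interval-censored between actual scan dates, while deaths and symptom-triggered progressions enter on their own dates. Reading the curve at week 30 instead is not advised: if 10 to 30% of patients reach C11D1 at least three weeks late, it shows 47-50% against a true 45%.
3. Reconcile the Cycle 2 label in 8.4.2 with 7.6(a) and footnote 6, so that the rPFS rule names the first bone scan actually performed.

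The cost is brief staff time, a few lines of code, and a protocol amendment with Protocol Review Committee and IRB approval (9.4). No extra scans or longer study are needed. The interval-censored estimate depends on its assumed shape; in the simulations it read 3 to 5 points high when the shape was wrong.
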